4.5 Measures

4.5.1 Primary measures

The primary effectiveness measure is the adherence (yes/no) of HF treatment to the current ESC guideline^{1, 2}. The following measures of HF therapy and concomitant medication will be used for derivation of the primary effectiveness measure:

- Active ingredient

- Single dose and dose unit
- Start and end date

Following the ESC guideline definitions, two levels of guideline adherence will be used for the analysis: adherence with respect to drug types (level 1) and adherence with respect to drug types **and** drug dose (level 2). The exact definitions of both levels of guideline adherence are provided in [Table 4-2](#).

Table 4-2 ESC guideline definitions

Guideline level	Criteria for guideline adherence
Drug types	Treatment with one [*] ACEi [°] or one [*] ARB ⁺ , in combination with one [*] beta-blocker ⁺ and one [*] MRA ⁺ for patients with an LVEF ≤ 35% at Visit 1 Treatment with one [*] ACEi [°] or one [*] ARB ⁺ , in combination with one [*] beta-blocker ⁺ without treatment with an MRA for patients with an LVEF > 35% at Visit 1
Drug type and dose	Guideline adherent with respect to drug types and dosage of all respective guideline drugs ≥ 50% of the recommended target dose [#]

^{*} exactly one

⁺ Only drugs with indication for treatment of HF will be considered as according to guidelines. Any use of a drug from the respective class with no indication for HF leads to treatment classified as non-adherent.

[°] Alternatively: Sacubitril/Valsartan

[#] In case a recommended target dose of a HF medication cannot be defined, the criterion for guideline adherence with respect to drug dose will be considered as fulfilled for this drug (independent from the actual dose)

For identification of the drugs relevant for guideline adherence the following implementations will be used:

- ACEi: ATC texts "ace inhibitors and diuretics", "ace inhibitors, plain"
- ARB: ATC texts "angiotensin ii antagonists and calcium channel blockers", "angiotensin ii antagonists and diuretics", "angiotensin ii antagonists, plain"
- Beta-blocker: ATC texts "alpha and beta blocking agents", "beta blocking agents, non-selective", "beta blocking agents, selective", "beta blocking agents, selective, and thiazides"
- MRA: ATC code C03DA

[Table 4-3](#) describes guideline relevant treatments with indication for HF and provides the respective target doses to be applied for the guideline analyses:

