Table 4-3 Recommended target doses used for guideline analyses

Treatment	Recommended total daily target dose (mg)
ACEi	
Benazepril	40
Captopril	150
Cilazapril	10
Enalapril	20
Fosinopril	80
Lisinopril	35
Perindopril	16
Quinapril	80
Ramipril	10
Trandolapril	4
Sacubitril/Valsartan*	194/206*
ARB	
Candesartan	32
Losartan	150
Valsartan	320
Beta-blocker	
Bisoprolol	10
Carvedilol	50
Metoprololsuccinat, Metoprolol	200
Nebivolol	10
MRA	
Eplerenone	50
Spironolactone	50

* Considered as (exactly) one treatment with combined total daily target dose of 400 mg.

The following drugs do not have an indication for HF and will yield the patient being classified as non-adherent: Moexipril (ACEi), Zofenopril (ACEi), Eprosartan (ARB), Irbesartan (ARB), Olmesartan medoxomil (ARB), Telmisartan (ARB), Atenolol (Beta-blocker), Betaxolol (Beta-blocker), and Sotalol (Beta-Blocker).

The HF indication and the daily target dose of any ACEi, beta-blocker, ARB or MRA neither included in this list nor in [Table 4-3](#) but occurring in the data (according to the above described implementations) will be identified separately and confirmed by Novartis.

In case the dose is not given in “total daily dose in mg”, it will be converted respectively.

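### The ATC texts that identify guideline drugs cover calcium-channel-blocker combinations for ARBs but not for ACE inhibitors, so adherence can be misclassified in either direction

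*SAP*

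**What the plan says.** SAP 4.5.1 sets the search rule: "For identification of the drugs relevant for guideline adherence the following implementations will be used". One list per class follows. The ACE inhibitor list reads "ACEi: ATC texts 'ace inhibitors and diuretics', 'ace inhibitors, plain" and stops there. The ARB list has the two corresponding entries and a third, "angiotensin ii antagonists and calcium channel blockers". MRAs are found by an ATC code.

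The same section names the data that feed the derivation: "The following measures of HF therapy and concomitant medication will be used for derivation of the primary effectiveness measure". Active ingredient is the first item listed. Non-HF medication is therefore in scope as well as HF therapy.

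After Table 4-3 the SAP provides for class members that are not tabulated. Their HF indication and target dose are settled with the sponsor, but the provision is limited to drugs missing from the tables "but occurring in the data (according to the above described implementations) will be identified separately".

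For sacubitril/valsartan, a footnote to Table 4-2 attached to the ACE inhibitor component says "Alternatively: Sacubitril/Valsartan". Table 4-3 lists the product in the ACE inhibitor block with the note "Considered as (exactly) one treatment with combined total daily target dose of 400 mg". No identification bullet mentions it.

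SAP 7.4.2 places the primary analysis on level 1 (drug types). SAP 2.5 makes the SAP's methods binding on programming.

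**The concern.** The primary variable is a yes/no classification built from drug-class membership. If the search misses a product, everything downstream treats the patient as not taking it. The ARB list shows that the authors meant calcium-channel-blocker combinations to count, and the SAP gives no reason for treating ACE inhibitors differently.

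The primary proportion is conditional: patients adherent at Visit 2 (A2) among those not adherent at Visit 1 (A1). An error at A1 changes who is in the denominator, and an error at A2 changes who is in the numerator. Level 2 requires level 1 to be met, so the dose-based analysis inherits the same errors.

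**Working it through.** **Step 1. Does another provision catch an unmatched ACE inhibitor combination?**

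| Provision | What it does | Closes the gap? |
|---|---|---|
| Sponsor review after Table 4-3 | Settles HF indication and target dose for drugs the ATC texts have found | No; an unmatched product never reaches it |
| Re-analysis ignoring HF indication (SAP 7.4.2) | Drops the indication rule | No; adds no ATC text |
| LVEF substitution (SAP 7.10) | Replaces missing LVEF | Unrelated |
| Coding (SAP 2.2) | ATC to level 4 and preferred name | Supplies the data for a repair, but no rule |

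The documents do not say which ATC text any given combination receives. That an ACE inhibitor with a calcium channel blocker falls outside the list is read from the wording of the two ACE inhibitor texts, neither of which describes it.

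**Step 2. Which way can the error run?**

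- *Read as absent.* The patient's only ACE inhibitor is unmatched, and an adherent regimen is classed as non-adherent.
- *Read as adherent.* Table 4-2 requires exactly one drug per component. If an unmatched ACE inhibitor is taken with a matched ARB, or with a second, matched ACE inhibitor, the search sees one drug where there are two. An unmatched product also escapes the rule that a class member without HF indication makes the patient non-adherent.

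**Step 3. Illustration of size.** No stated figure is in dispute, so the protocol's planning values (section 9.8) serve only as a scale: 2,160 referred and 20% adherent at baseline, giving 2,160 × 0.20 = 432 adherent and 1,728 not. A 25% switch gives 0.25 × 1,728 = 432 switchers (the two 432s coincide by chance) and 1,296 who remain non-adherent. The 95% half-width is 1.96 × √(0.25 × 0.75 / 1,728) = 0.0204, in line with the protocol's ±2%.

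Let f be the share of truly adherent regimens read as non-adherent, and g the share of the 1,296 read as adherent. Both are assumptions. Patients adherent at baseline are taken to be adherent at Visit 2 as well.

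| Route | Formula | 1% | 2% | 5% | 10% |
|---|---|---|---|---|---|
| Absent, both visits | 432(1−f)/(1,728+432f) | 24.7% | 24.4% | 23.5% | 22.0% |
| Absent, Visit 2 only | 432(1−f)/1,728 | 24.8% | 24.5% | 23.8% | 22.5% |
| Absent, Visit 1 only | (432+432f)/(1,728+432f) | 25.2% | 25.4% | 25.9% | 26.8% |
| Adherent, both visits | 432/(1,728−1,296g) | 25.2% | 25.4% | 26.0% | 27.0% |
| Adherent, Visit 2 only | (432+1,296g)/1,728 | 25.8% | 26.5% | 28.8% | 32.5% |

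The third row matters: even the read-as-absent error raises the proportion if a patient moves from an unmatched to a matched product, because that patient then appears as a switch. In the first row the bias reaches 2 points at f of about 6.5%: 432 × 0.935 / (1,728 + 28.1) = 0.230.

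**The case against.** **The gap may be empty.** The SAP cites a data validation plan dated 20 March 2018 and reports last patient last visit on 23 March 2018, so its authors may have built the lists from what was recorded. The beta-blocker list supports this: it includes selective agents combined with thiazides and has no non-selective counterpart. If no ACE inhibitor with calcium channel blocker was recorded, the omission has no effect. This is possible, but the SAP does not say that the lists came from the data, and a check would settle it.

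**A programmer could work from active ingredient.** It is a listed input, and Table 4-3 names the ACE inhibitors. However, the SAP states the search rule in terms of ATC texts and introduces Table 4-3 as the source of target doses. Two programmers could reasonably proceed differently, so the binding text should choose.

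**Sacubitril/valsartan.** A reader might infer that patients moved to it would be classed as lacking the drug. The documents do not support that. Both tables name it, place it in the ACE inhibitor slot and say how to count it, so a programmer following the SAP must credit it. Nor do the documents give the ATC text it is coded to. What remains is that no text, code or preferred name links it to the search rule.

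**The illustration is not evidence.** This stands. The shares are assumed, and the 25% is a planning value for adherence with a dose threshold, whereas the primary analysis uses drug type alone. Recruitment also stopped early, so the planned counts are not those to be analysed.

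**Conclusion.** The point holds as a gap in the stated rule. The identification list is closed, it treats ACE inhibitors and ARBs differently without a reason, and no other provision reaches an unmatched product. Misclassification at A1 or A2 is possible in the primary analysis and carries through to level 2.

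A reader might infer that the estimate is biased downwards. The documents do not support a sign: the exactly-one rule and a move between unmatched and matched products both push the proportion upwards. They do not support a size either, because they give no frequency for these products. On planning values, and if the first route alone operated, about 6.5% of adherent regimens would have to be unmatched at both visits before the bias matched the planned ±2% precision. Nothing in the documents shows whether the true share is near that.

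The case for acting is that the variable is primary, the rule is binding, and the repair is cheap. For sacubitril/valsartan the finding is only a missing identification term.

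**What to change.** In SAP 4.5.1, or by the addendum that SAP 7.12 allows:

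1. Identify each class by active ingredient or preferred name, in single and fixed-combination products alike. Alternatively, add the missing ACE inhibitor combination texts.
2. Identify sacubitril/valsartan explicitly by preferred name, as exactly one treatment in the ACE inhibitor slot and never also as an ARB. Without this exception an ingredient rule would count its valsartan component a second time, because valsartan is itself a Table 4-3 ARB, and could upset the exactly-one test.
3. Keep the ATC texts as a cross-check and list every disagreement between the two methods.
4. Before analysis, extend the sponsor review to HF and concomitant cardiovascular products that the texts leave unmatched, and report how many patients are reclassified at each visit.

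The cost is revised wording, a one-off look-up and the review of a product list. Active ingredient and preferred name are already in the data, so no new collection is needed. If the review finds no unmatched product, the results do not change and the report can say so.

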4.5.2 Secondary measures

EuroQol five dimensions five levels questionnaire (EQ-5D-5L)

The EQ-5D is a non-disease specific, validated and widespread instrument for quantifying the life quality of adult patients. The measure is divided into two distinct sections. The first section includes five rating scales addressing each of five dimensions (mobil-

ity, self-care, usual activity, pain/discomfort, and anxiety/depression). The second section includes a self-rated (global) health status measurement utilizing a vertically oriented visual analogue scale where 100 represents the “best possible health state” and 0 represents the “worst possible health state”.

In the current study the EQ-5D-5L version of the questionnaire is used. In this version the extent of problems in each single life quality dimension can be assessed by five levels: no problems, slight problems, moderate problems, severe problems, inability in the respective dimension.

The EQ-5D-5L utility index is derived to summarize the information of the five life quality dimensions. For this, a weighted mean with level- and dimension-specific weights (i.e. a specific value set) is calculated. For this analysis, the EQ-5D-5L value set for the UK (<https://euroqol.org/eq-5d-instruments/eq-5d-5l-about/valuation/>; Devlin et al., 2016) is used. Weights for each dimension and each level of problem are defined as follows (the weight for the category “no problems” within any dimension is set to 0):

- Mobility:
 - slight: 0.051
 - moderate: 0.063
 - severe: 0.212
 - unable: 0.275
- Self-care:
 - slight: 0.057
 - moderate: 0.076
 - severe: 0.181
 - unable: 0.217
- Usual activities:
 - slight: 0.051
 - moderate: 0.067
 - severe: 0.174
 - unable: 0.190
- Pain/discomfort:
 - slight: 0.060
 - moderate: 0.075
 - severe: 0.276
 - extreme: 0.341
- Anxiety/depression:
 - slight: 0.079
 - moderate: 0.104
 - severe: 0.296
 - extreme: 0.301

The utility index will be calculated as $1 - 0.9675 \times \sum(\text{weight of each dimension})$. Values of this index can range between -0.281 and 1.0 where a higher number indicates a better health status.

Kansas City Cardiomyopathy Questionnaire (KCCQ)

The KCCQ is a HF-specific questionnaire and requires on average 4-6 minutes to complete. It covers physical function, clinical symptoms, social function, self-efficacy and

knowledge, and QoL. The following KCCQ domains will be calculated for this study: physical limitation, symptom stability, symptom frequency, symptom burden, self-efficacy, QoL, and social limitation. Each subscore is transformed to a 0–100 scale, with higher score indicating higher level of functioning. A score of 100 represents perfect health whereas a score of 0 represents the worst condition. A clinical summary score is built by the mean of the physical limitation and total symptom scores. The total symptom score is calculated as the mean of the symptom frequency and symptom burden scores. Below are the calculation rules for each score:

- Physical Limitation. Physical Limitation Score = $100 * [(\text{mean of questions 1a-f actually answered}) - 1] / 4$
- Symptom stability
 - If question 2 was answered with 6 (=no symptoms over the last 2 weeks) this will be transferred to 3 (=not changed).
 - Symptom stability score = $100 * [(\text{Question 2}) - 1] / 4$
- Symptom frequency. Symptom Frequency is computed based on the following standardization:
 - $S3 = [(\text{Question 3}) - 1] / 4$
 - $S5 = [(\text{Question 5}) - 1] / 6$
 - $S7 = [(\text{Question 7}) - 1] / 6$
 - $S9 = [(\text{Question 9}) - 1] / 4$;
 - Symptom frequency score = $100 * (\text{mean of } S3, S5, S7 \text{ and } S9)$
- Symptom burden. Symptom burden score = $100 * [(\text{mean of questions 4, 6 and 8 actually answered}) - 1] / 4$
- Self-efficacy. Calculated as = $100 * [(\text{mean of questions 10 and 11}) - 1] / 4$
- QoL. Calculated as $100 * [(\text{mean of questions 12, 13 and 14 actually answered}) - 1] / 4$
- Social limitation. Calculated as $100 * [(\text{mean of questions 15a to 15d actually answered}) - 1] / 4$
- Total symptom score = mean of the following available summary scores:
 - Symptom frequency score
 - Symptom burden score
- Clinical summary score = mean of the following available summary scores:
 - Physical limitation score
 - Total symptom score

5 Analysis data sets

Only patients for whom all core Baseline characteristics are available will be included in the final analysis; core Baseline characteristics are defined as: gender, year of birth, NT-proBNP.

For all patients fulfilling these selection criteria, the following analysis sets will be defined:

- Analysis of Baseline variables will be carried out in all patients who signed the study information consent (Enrolled Set).

- Analysis regarding the prospective period of the study will be carried out on all patients entering into this study period, i.e. patients who were referred to the cardiologist – the respective patient set will be labelled Follow-up Set.

6 Variables of analysis

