6.6.2 Patient Reported Outcomes (PRO)

The impact of the disease per se (in all patients) and of CHF treatment optimization (in patients in the prospective period) on health related quality of life (QoL) will be assessed by the following measures:

- EuroQol EQ-5D (EQ-5D-5L)
- Kansas City Cardiomyopathy Questionnaire (KCCQ)

Both questionnaires are available as validated translations in local language.

The patient should be given sufficient instruction, space, time and privacy to complete the questionnaire. The study coordinator should check the responses to the questionnaire for completeness and encourage the patient to complete any missing responses.

As treatment optimization can affect all derived scores and subscales of both questionnaires, the change from baseline for all measures and scales derived from both questionnaires will be analyzed for patients who enter the prospective period of the study.

For patients who are not clinically stable or show NT-proBNP levels < 600 pg/ml only the baseline QoL will be documented.

The patients' responses shall be entered into the CRF by the investigator. The original questionnaire will be kept with the patient's file as the source document.

Completed questionnaires will be reviewed and examined by the investigator, before the clinical examination, for responses that may indicate potential adverse events (AEs) or serious adverse events (SAEs). The investigator should review not only the responses to the questions in the questionnaires but also for any unsolicited comments written by the patient. If AEs or

[figure not shown]
SAEs are confirmed, then the physician must record the events as per instructions given in [Section 7.1](#) and [Section 7.2](#) of the protocol.

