- Acceptance of cardiologist's advice on patient level (All changes implemented, No changes implemented, Changes partially implemented).
- Reason for non-acceptance of the cardiologist's advice

Patient reported outcomes

- EQ-5D VAS at Visit 1, Visit 2, Visit 3, absolute change from Baseline to Visit 2 and Visit 3 and absolute change from Visit 2 to Visit 3 (change calculated via *post minus pre value*).
- EQ-5D utility index at Visit 1, Visit 2, Visit 3, absolute change from Baseline to Visit 2 and Visit 3 and absolute change from Visit 2 to Visit 3 (change calculated via *post minus pre value*).
- EQ-5D single dimensions at Visit 1, Visit 2 and Visit 3.
- KCCQ sub-scores, total symptom score and clinical summary score at Visit 1, Visit 2, Visit 3, absolute change from Baseline to Visit 2 and Visit 3 and absolute change from Visit 2 at Visit 3 (change calculated via *post minus pre value*).

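### The SAP takes differences between visits of the KCCQ symptom stability score, which is itself a rating of recent change, so these change values are not changes in health and can have the wrong sign

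*SAP*

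**What the plan says.** SAP 4.5.2 lists the KCCQ domains to be calculated as "physical limitation, symptom stability, symptom frequency, symptom burden, self-efficacy, QoL, and social limitation". Symptom stability uses question 2 only: subtract 1, divide by 4, multiply by 100. Before scoring, one answer is recoded: "If question 2 was answered with 6 (=no symptoms over the last 2 weeks) this will be transferred to 3 (=not changed".

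The same section describes all sub-scores alike: "Each subscore is transformed to a 0–100 scale, with higher score indicating higher level of functioning", and "A score of 100 represents perfect health whereas a score of 0 represents the worst condition". It makes no exception for symptom stability.

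SAP 6.2 lists as variables "KCCQ sub-scores, total symptom score and clinical summary score at Visit 1, Visit 2, Visit 3, absolute change from Baseline to Visit 2" and to Visit 3, and also the change from Visit 2 to Visit 3, each as post minus pre. SAP 7.7 carries these variables into the analysis. Protocol 6.6.2 plans the same for the prospective period: "the change from baseline for all measures and scales derived from both questionnaires will be analyzed". Protocol Table 2-1 names change in the individual KCCQ sub-scores between visits as an endpoint. SAP 7.13, which records departures from the protocol, has no entry on the KCCQ.

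**The concern.** The printed labels show what question 2 measures. Its middle answer means that symptoms have not changed, and its sixth answer, for patients without symptoms over two weeks, is moved to that middle position. The score therefore says which way symptoms have recently moved, not how good or bad they are. The other sub-scores are levels, and subtracting one level from another gives a change. Subtracting one change rating from another gives something closer to a change in the rate of change.

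The visit schedule makes the awkward pattern plausible. Protocol 3.1 suggests Visit 2 within 4 weeks after the cardiologist visit, so a short recall at Visit 2 can catch a fresh improvement. Visit 3 follows at least 3 months later, so a patient who has kept the benefit would then report no change or no symptoms. The course of quality of life after referral is a secondary objective. For such patients the Visit 2 to Visit 3 change in this sub-score would read as a loss.

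**Working it through.** **Inputs.** From SAP 4.5.2: score = 100 × (Q2 − 1)/4, with Q2 = 6 first set to 3; answer 3 means not changed. From SAP 6.2: changes are post minus pre for Visit 2 − Baseline, Visit 3 − Baseline and Visit 3 − Visit 2.

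**Assumptions.** The SAP prints labels only for answers 3 and 6. That 5 is the most improved answer and 1 the most worsened follows from the stated direction (higher is better), but is an inference. The two-week recall is attached in the SAP to answer 6; I take it to apply to the whole item.

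**Step 1, the SAP's stated range.** Q2 = 1, 2, 3, 4, 5 gives 0, 25, 50, 75, 100, so the 0 to 100 range is reproduced. Without the recode, answer 6 would give 100 × (6 − 1)/4 = 125, outside the range. With it, answer 6 gives 100 × (3 − 1)/4 = 50.

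**Step 2, changes for example answer patterns.**

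| Q2 at Visits 1, 2, 3 | Reading | Scores | V2 − BL | V3 − BL | V3 − V2 |
|---|---|---|---|---|---|
| 3, 5, 3 | improved by Visit 2, then unchanged | 50, 100, 50 | +50 | 0 | −50 |
| 3, 5, 6 | improved by Visit 2, then symptom-free | 50, 100, 50 | +50 | 0 | −50 |
| 3, 4, 3 | smaller improvement, then unchanged | 50, 75, 50 | +25 | 0 | −25 |
| 3, 5, 5 | improving at both visits | 50, 100, 100 | +50 | +50 | 0 |
| 3, 3, 6 | symptom-free at Visit 3 | 50, 50, 50 | 0 | 0 | 0 |
| 5, 3, 6 | improving at Baseline, then unchanged, then symptom-free | 100, 50, 50 | −50 | −50 | 0 |
| 1, 3, 3 | worsening at Baseline, then unchanged without recovery | 0, 50, 50 | +50 | +50 | 0 |

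**Step 3, when the sign is wrong.** In rows 1 to 3 and in rows 6 and 7, the reported change falls at the earlier of the two visits compared, and the later visit reports none. The difference then reverses the direction first reported. Where an improvement happens between visits and outside the recall period, as it may in row 5, the difference is 0 and the improvement is missed rather than reversed.

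**Step 4, what else uses the score.** By SAP 4.5.2 the total symptom score is the mean of symptom frequency and symptom burden, and the clinical summary score is the mean of physical limitation and total symptom score. Symptom stability enters neither.

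**The case against.** The strongest reply is that little depends on this score. The analysis is descriptive, no test or responder rule uses symptom stability, and SAP 6.2 also reports the score at each visit, so a careful reader would see 50, 100, 50 and not only −50. The same plan reports symptom frequency, symptom burden, physical limitation, both KCCQ summary scores and the EQ-5D measures, all of which describe levels. That stands, and it limits the weight of the point.

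Stronger readings that a reader might infer do not hold:

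- That the recode of 6 to 3 is a scoring error because a symptom-free patient gets only 50. For a change item the recode is coherent, and it keeps the score within range. The fault lies in the sentence equating 100 with perfect health, which cannot apply to this sub-score.
- That every patient who improves and stays well is shown as deteriorating. This needs the improvement to be reported at the earlier visit compared. Under Protocol 3.1 the primary care physician settles future treatment at Visit 2, and an improvement from a change first made there comes later. The documents give no basis for estimating how many patients would show the pattern.
- That −25 or −50 can be set against the 5-point minimal improvement. Protocol 9.5.1 defines that threshold only for physical limitation and total symptom score.

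Protocol 9.5.1 also limits KCCQ analysis to domains on symptoms and physical limitation. That does not clearly exclude symptom stability, and the SAP calculates it in any case, so it does not remove the problem.

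**Conclusion.** The concern holds in this limited form. As written, SAP 6.2 requires change values for symptom stability that do not measure change in health. They can show −25 or −50 from Visit 2 to Visit 3 when a gain was kept, 0 from Baseline for the same patients, and +50 when a worsening at Baseline was never recovered. This rests on reading question 2 as a change item, which its printed labels support, and on the inferred order of answers 1, 2, 4 and 5.

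The effect is confined to one descriptive secondary sub-score. A reader might infer that the quality-of-life objective as a whole is compromised. The documents do not support that, because the remaining scales are unaffected, as are the KCCQ summary scores and the primary analysis. It is still worth correcting, because following the stated rule produces figures that can mislead and the correction is cheap.

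**What to change.** 1. In SAP 6.2 and 7.7, exclude symptom stability from the changes from Baseline and from Visit 2. Report it per visit only, either as the score or, more readably, as frequencies of the question 2 answers with code 6 shown separately.
2. In SAP 4.5.2, limit the sentence on the meaning of 100 and 0 to the other sub-scores, and say that 50 on symptom stability means no change.
3. In SAP 7.13, list the departure from Protocol 6.6.2 and Table 2-1, which call for change on all scales and sub-scores. The same entry can state how Protocol 9.5.1, with its narrower set of KCCQ domains, is being read.

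The cost is SAP wording, one table shell and one entry in the list of deviations. No new data are needed, since Protocol 6.6.2 already has the patients' responses entered in the CRF.

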9.5.1 Patient reported outcomes

Health related quality of life as measured by the patient reported outcomes EQ-5D-5L and KCCQ.

The KCCQ instrument includes several domains. Only the domains that address HF symptoms and physical limitations will be analyzed. The clinical summary score of KCCQ is computed as the mean of the following available domain scores:

- Physical limitation score
- Total HF symptom score

Minimal clinical improvement according to the KCCQ will be defined for each of the two domain scores as an improvement of at least 5 points compared to baseline ([Flynn, Lin et al. 2012](#)).

The EQ-5D-5L consists of five domains and one visual analogue scale. This instrument assesses morbidity, self-care, usual activity, pain, and anxiety and depression of patients on a five-point rating scale ranging from *1=no problems* to *5=extreme problems*. A continuous utility index will be derived from these dimensions.

Quantitative outcomes such as KCCQ sub-domains, EQ-5D visual analogue scale and EQ-5D utility index will be displayed in terms of descriptive statistical parameters such as valid n, mean, SD, minimum, median and maximum at each visit.

Furthermore, for visit 2 the change from baseline and for visit 3 the change from baseline and from visit 2 will be calculated and displayed.

In case of ordinal or dichotomous measures such as EQ-5D dimensions and KCCQ response distributions in terms of absolute and relative frequencies will be provided for the single visits.

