7.10 Missing data and outliers

In General, no imputation of missing data will be performed for analysis of the primary variable. This means that for patients with missing LVEF at Baseline the primary variable is not evaluable. Instead, proportions based on observed data and proportions including patients with missing data will be provided (see [Section 7.4.2](#)). However, for reason of sensitivity the analyses of guideline adherence (only analyses taking into account the HF indication of treatments) will be repeated by applying the following substitution: missing LVEF values will be replaced by LVEF category “> 35%”.

Missing values in single items of patient questionnaires will be treated according to the descriptions in [Section 4.5.2](#). Changes from Baseline cannot be calculated if either the data at Visit 1 or after Visit 1 are missing: no replacement of missing data will be performed in such cases.

Incompletely reported date variables will be imputed as follows: if day is not given, the 15th of the month will be imputed, if month is not given the 1 July of the respective year will be used for analysis. If these imputations lead to negative values when calculating durations, the respective duration will be set to one day.

Any impossible / implausible values not identified during data management processes will be treated as missing and not to be imputed

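### KCCQ total symptom and clinical summary scores average whichever components are available, so a change score can compare different components at two visits and show a false change in an unchanged patient

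*SAP*

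**What the plan says.** SAP 4.5.2 gives the KCCQ scoring rules. Physical limitation, symptom burden, quality of life and social limitation are scored from the items that were answered; for burden the wording is "mean of questions 4, 6 and 8 actually answered". No minimum number of answered items is set. Symptom frequency is 100 times the mean of the four rescaled items S3, S5, S7 and S9, without the answered-items wording.

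The two higher-level scores are then defined as "Total symptom score = mean of the following available summary scores" (symptom frequency and symptom burden) and "Clinical summary score = mean of the following available summary scores" (physical limitation and total symptom). Protocol 9.5.1 has the same rule for the second: "The clinical summary score of KCCQ is computed as the mean of the following available domain scores".

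On missing data, SAP 7.10 states: "Missing values in single items of patient questionnaires will be treated according to the descriptions in" section 4.5.2. It adds only this limit on change scores: "Changes from Baseline cannot be calculated if either the data at Visit 1 or after Visit 1 are missing". SAP 6.2 lists as analysis variables "KCCQ sub-scores, total symptom score and clinical summary score at Visit 1, Visit 2, Visit 3, absolute change from Baseline" to Visits 2 and 3, and from Visit 2 to Visit 3.

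Protocol 9.5.1 sets a minimal clinical improvement of at least 5 points from baseline for the physical limitation score and the total HF symptom score.

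**The concern.** The introductory text of SAP 4.5.2 describes the total symptom score as the mean of frequency and burden. The availability rule lets one of the two stand in for the pair. If a frequency item is blank at one visit and the rule is applied as written, the score is frequency and burden together at one visit and burden alone at the other. The score is not missing, so the limit in SAP 7.10 does not apply and a change is calculated. The difference in level between the two domains is then recorded as a change in health.

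These change scores are how the study describes the course of quality of life after referral. Total symptom score is also one of the two scores to which the protocol attaches its 5-point criterion.

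**Working it through.** The plan gives no figure to reproduce here, so the check applies the SAP 4.5.2 formulas directly. Write F for symptom frequency, B for burden and PL for physical limitation.

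**Effect of losing F at one visit**
- Total symptom score goes from (F + B)/2 to B. False change = (B − F)/2.
- Clinical summary score goes from [PL + (F + B)/2]/2 to (PL + B)/2. False change = (B − F)/4. PL cancels.
- If F is lost at the earlier visit instead, the sign reverses.

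**Worked record, same health at both visits**
- Questions 3, 5, 7, 9 answered 3, 4, 4, 3: F = 100 × mean(2/4, 3/6, 3/6, 2/4) = 50.0.
- Questions 4, 6, 8 answered 4, 4, 3: B = 100 × (11/3 − 1)/4 = 66.7.
- All six physical limitation items answered 3: PL = 50.0.
- Complete: total symptom = (50.0 + 66.7)/2 = 58.3; clinical summary = (50.0 + 58.3)/2 = 54.2.
- Question 9 skipped at the later visit: total symptom = 66.7 (**+8.3**); clinical summary = (50.0 + 66.7)/2 = 58.3 (**+4.2**).

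**Gap needed for a false change of 5 points**
- Total symptom: |B − F|/2 ≥ 5, so a gap of 10. One response step on one burden item moves B by 100 × (1/3)/4 = 8.3, so 10 is not a large gap.
- Clinical summary: |B − F|/4 ≥ 5, so a gap of 20.

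**Share of mismatched pairs reaching 5 points in total symptom score**

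Assumption, not in the documents: in unchanged patients B − F is normal with mean 0 and the SD shown. False improvement has probability 1 − Φ(10/SD); either direction is twice that.

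| SD of gap | False improvement ≥ 5 | Either direction |
|---|---|---|
| 10 | 16% | 32% |
| 15 | 25% | 50% |
| 20 | 31% | 62% |

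The mean of the false change is 0 under this assumption.

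**If the programmer averages the answered frequency items instead**
- In the record above, skipping question 9 changes total symptom score by 0.0.
- With questions 3, 5, 7, 9 = 4, 5, 5, 4 and questions 4, 6, 8 = 4, 4, 5, the change is −0.7, against +6.25 when F is dropped.

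**No minimum number of items**

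Physical limitation answers 5, 5, 4, 3, 2, 2 give 100 × (3.5 − 1)/4 = 62.5. If only the first two items are answered, the same patient scores 100. This needs four of six items blank, so it is an extreme case, but nothing in the rule excludes it.

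**The case against.** The strongest reply is that losing symptom frequency depends on one reading. The formula does not say what happens when an item is blank, and a programmer who averages the answered items nearly removes the effect. That stands: the text is ambiguous. But the answered-items wording appears for four other domains and not for this one, and SAP 2.5 makes the SAP methods mandatory for programming. Two programmers could reasonably get different scores from the same record.

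The availability rule is also prespecified in Protocol 9.5.1, so for the clinical summary score the SAP follows the protocol. That is so, but neither document says what to do when the available components differ between visits.

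Missing items should also be uncommon. Protocol 6.6.2 has the coordinator check completeness and encourage missing answers, and Protocol 8.2 and SAP 2.5 add data checks. These reduce blank items but do not exclude them.

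A reader might infer three stronger things that the documents do not support.
- **That the mean course of quality of life is biased.** This would need an average gap away from zero and unequal loss of frequency between visits. Neither is shown.
- **That 32% to 62% of mismatched pairs meet the protocol's criterion.** That range counts false worsening too. The criterion is improvement, so 16% to 31% applies. SAP 6.2 lists no 5-point KCCQ responder variable, although Protocol Table 2-1 mentions responders and SAP 7.13 does not declare them dropped.
- **That a number of affected patients can be given.** Item-missing rates of 1% to 3%, independent across items and visits, would give 7.6% to 20.3% of pairs mismatched: p = 1 − (1 − m)^4, then 2p(1 − p). Both the rates and the independence are assumptions, and a patient who skips the same item at both visits creates no mismatch. The 2,160 of Protocol 9.8 is a planned number; SAP 4.2 says recruitment and data collection stopped early.

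**Conclusion.** The point holds as a low-cost improvement to the scoring rules. Under the literal reading, one skipped frequency item at one visit produces a false change of half the burden-minus-frequency gap in total symptom score and a quarter of it in clinical summary score. A 10-point gap is enough for a false 5-point change in total symptom score. Clinical summary needs 20 points, and the protocol's 5-point criterion does not cover that score.

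The 16% to 31% figure applies only to mismatched pairs and rests on an assumed gap with mean 0 and SD 10 to 20. How often pairs would be mismatched cannot be determined from the documents. What has been shown is added noise and false individual changes in secondary, descriptive outcomes. The primary endpoint, guideline adherence, does not use these scores.

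**What to change.** Amend SAP 4.5.2 and 7.10 in two places.

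1. Score every multi-item domain, including symptom frequency, from the answered items, subject to one stated minimum, for example at least half. The one-half figure is a suggestion and not taken from the documents; what matters is that one minimum is stated and applied throughout. On its own this shrinks the artefact but need not remove it, as the −0.7 above shows.
2. For each pair of visits, calculate change in total symptom and clinical summary scores only from components scored at both visits, and otherwise set the change to missing. The artefact from a dropped component is then exactly zero.

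The cost is a few lines of SAP text and programming; no new data are needed. Rule 1 changes some per-visit domain scores and makes a few missing, where they rest on one or two items. Under rule 2 a change may not equal the difference between the two per-visit summary scores, which a table footnote should say.
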